16.2.2.3. Analysis of the Secondary Endpoints

GOS-E at Day 180

GOS-E at Day 180 will be analyzed as a 7-category ordinal scale (1/2, 3, 4, 5, 6, 7, and 8) using ordinal logistic regression, adjusting for covariates including all the stratification factors at randomization and baseline contusion volume per the central review and baseline GCS. Multiple imputation will be used to account for missing GOS-E at Day 180.

mRS at Day 90

mRS at Day 90 will be analyzed as a 5-category ordinal scale (0/1, 2, 3, 4, and 5/6) using ordinal logistic regression, adjusting for covariates including all the stratification factors at randomization, baseline contusion volume per the central review, and baseline GCS.

Proportion of participants requiring delayed intubation

The proportion of participants requiring delayed intubation at any time between 24 hours and 96 hours post injury or LKN will be analyzed at Day 4. The analysis will compare BIIB093 (3 mg/day or 5 mg/day) and placebo groups using a binary logistic regression, adjusting for covariates including all the stratification factors at randomization and baseline contusion volume per the central review and baseline GCS.

Change in total contusion volume (hematoma plus perihematomal edema) from baseline to 24 hours

An ANCOVA model will be used to compare BIIB093 (3 mg/day or 5 mg/day) and placebo groups, adjusting for covariates including all the stratification factors at randomization, and baseline contusion volume per the central read. This endpoint will be evaluated for all participants having a scan acquired between 12 hours after the initiation of study treatment and the end of the Hour 24 Visit. Summary statistics, including by-visit number of participants with data, mean, SD, median, quartiles, and range will be provided.

CONFIDENTIAL

The information contained herein may not be used, disclosed, or published without the written consent of
Biogen MA Inc.

Change in absolute hematoma volume from baseline to 24 hours

Analysis of covariance (ANCOVA) will be performed to compare the mean change from baseline between BIIB093 (3 mg/day or 5 mg/day combined) and placebo groups. This endpoint will be evaluated for all participants having a scan acquired between 12 hours after the initiation of study treatment and the end of the Hour 24 Visit. Summary statistics, including by-visit number of participants with data, mean, SD, median, quartiles, and range will be provided.

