Change in absolute edema volume from baseline to 96 hours

ANCOVA will be performed to compare the mean change from baseline between BIIB093 (3 mg/day or 5 mg/day) and placebo groups. This endpoint will be evaluated for all participants having a scan acquired between 12 hours after the initiation of study treatment and the Hour 96 Visit. Multiple imputation will be used to account for missing values for the Hour 96. Summary statistics, including by-visit number of participants with data, mean, SD, median, quartiles, and range will be provided.

Time to all-cause death, including neurological death, through Day 90

Survival time will be analyzed for all randomized participants. Cox proportional hazards regression models will be used to assess the treatment effects on overall survival at Day 90 after adjusting for covariates including the stratification factors at randomization, baseline contusion volume per the central review, and baseline GCS. Kaplan-Meier curves will be presented for BIIB093 (3 mg/day or 5 mg/day) and placebo groups.

CONFIDENTIAL

The information contained herein may not be used, disclosed, or published without the written consent of Biogen MA Inc.

[REDACTED]

[REDACTED]

[REDACTED]

[REDACTED]

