### **5.3.2. Baseline Disease Characteristics per CRFs**

- Time (hours) to randomization post injury or LKN
- Time (hours) to initiation of study drug infusion post injury or LKN
- Time (hours) to NCCT for eligibility post injury or LKN
- Time (hours) to initiation of study drug infusion from NCCT for eligibility
- Injury types
- Baseline GCS before randomization
- Total injury severity scoring (ISS) score excluding head or face
- Baseline brain contusion volume (mL) per investigator
- Baseline brain contusion volume (mL) per the central review
- Baseline hematoma volume (mL) per the central review
- Baseline edema volume (mL) per the central review
- Baseline blood glucose
- Baseline alcohol level
- Baseline sodium

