### 5.6.1. General Analysis Methods for Efficacy Endpoints

All endpoint models (binary logistic regression, ordinal logistic regression, Cox model, and analysis of covariance) below will regress the outcome on the randomized treatment group, comparing the BIIB093 combined with placebo groups, adjusting for all the IRT stratification factors at randomization (see [Section 3.5.1](#)), baseline contusion volume per the central review and baseline GCS.

Analysis of covariance (ANCOVA) will be performed to compare the change in total contusion volume (primary analysis), change in absolute hematoma volume, the change in absolute edema volume, [REDACTED] from baseline in the main analysis comparing the BIIB093 combined with placebo groups. The least square (LS) mean difference with the corresponding 2-sided 95% CI and p-values for the treatment group will be provided.

Binary logistic regression will be used for binary outcomes comparing the BIIB093 combined with placebo groups. Odds ratio, the corresponding 2-sided 95% confidence interval (CI) and p-value will be reported for the treatment group.

Ordinal logistic regression (proportional odds model) will be used for GOS-E as a 7-category ordinal scale (1/2, 3, 4, 5, 6, 7, 8) and for mRS as a 5-category ordinal scale (0/1, 2, 3, 4, 5/6) at Day 90 and 180. Odds ratio, the corresponding 2-sided 95% CI and p-value for the treatment group will be reported.

The proportional odds ratio assumption will be tested using likelihood ratio test based on observed data. In the case the assumption does not hold (p-value < 0.05) or non-convergence, the Mann-Whitney test will be used as the primary inference and the source of non-proportionality or non-convergence will be investigated. Following the Mann-Whitney test, dichotomized analysis will be conducted to assess the treatment effects.

The Cox proportional hazard model will be used to assess the treatment effect on overall survival at Day 90 for all randomized participants. Hazard ratio, 2-sided 95% CI as well as the p-value for the treatment group will be reported. Kaplan-Meier curves will be presented by randomized treatment group, and Greenwood's formula will be used to calculate the standard error of the Kaplan-Meier estimates.

Multiplicity will be not be adjusted for the tests of the primary and secondary endpoints, since the current study sample size is not powered for a moderate treatment effect on GOS-E.

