### **Change in Absolute Hematoma Volume from Baseline to 24 Hours**

Change in absolute hematoma volume from baseline to 24 hours will be analyzed in the Day 4 database for the full analysis set.

- ANCOVA will be performed to compare the mean change between BIIB093 combined and placebo groups based on the observed data.
- By-visit mean and change in absolute hematoma volume from baseline will be summarized.

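### The hematoma-change and edema-change ANCOVAs adjust for baseline total contusion volume but not for the endpoint's own centrally read baseline; this can cost precision but does not bias the comparison

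*SAP*

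**What the plan says.** The covariate rule in SAP 5.6.1 is general: "All endpoint models (binary logistic regression, ordinal logistic regression, Cox model, and analysis of covariance) below will regress the outcome" on randomized treatment, adjusting for the IRT stratification factors, "baseline contusion volume per the central review and baseline GCS". The next paragraph of that section names the "change in absolute hematoma volume, the change in absolute edema volume" among the ANCOVA analyses, so both component endpoints fall under the rule.

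The endpoint text in SAP 5.6.3 adds no covariate. For hematoma it reads "ANCOVA will be performed to compare the mean change between BIIB093 combined and placebo groups based on the observed data", and the edema text is the same.

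Protocol 16.2.2.3 names no covariates for these two endpoints. For hematoma, ANCOVA "will be performed to compare the mean change from baseline between BIIB093 (3 mg/day or 5 mg/day combined) and placebo groups"; for edema, "ANCOVA will be performed to compare the mean change from baseline between BIIB093 (3 mg/day or 5 mg/day) and placebo groups".

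The component baselines exist. SAP 5.3.2 lists "Baseline hematoma volume (mL) per the central review" and "Baseline edema volume (mL) per the central review" among the baseline characteristics, and SAP 3.5.2 uses both as median-split subgroup variables. In the readable text they enter no efficacy model, and SAP 5.1 makes the subgroup analyses unadjusted.

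The primary endpoint and the 24-hour total-volume endpoint are adjusted for centrally read baseline total volume, that is, for their own baseline (Protocol 16.2.2.2 and 16.2.2.3; SAP 5.6.1).

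**The concern.** ANCOVA on a change score usually conditions on the baseline of the variable being measured. Here each component is conditioned on the sum. Take two participants with 20 mL in total, one with 18 mL hematoma and 2 mL edema, the other with 8 and 12. They receive the same volume adjustment although they start far apart on the measured component.

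These two endpoints, with 24-hour total change, serve the secondary objective of telling an effect on bleeding from an effect on edema. Randomization is stratified on total volume only (SAP 3.5.1), so nothing beyond chance balances the hematoma/edema split between arms. If the split affects later change, leaving it out widens the confidence intervals, and a chance imbalance passes uncorrected into the two comparisons.

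**Working it through.** **1. The plan's own figure.** The only power statement concerns the primary endpoint: 80 against 80, SD 29 mL, difference 15 mL, two-sided 5% (Protocol 16.8, SAP 2.3). 15 / (29 × √(2/80)) = 3.271; 3.271 − 1.960 = 1.311; Φ(1.311) = 0.905. The noncentral t with 158 df gives 0.902. The stated figure of about 90% reproduces and is not in question. No SD, effect size or power is given for hematoma or edema change.

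**2. General size of the gain.** Let r be the partial correlation of the change with its own baseline, given the planned covariates. Adding that baseline multiplies residual variance by 1 − r², a reduction of r². The values of r are assumed. The last column assumes 80% power under the planned model.

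| r | Variance ratio | CI width ratio | Equivalent to raising N = 160 to | Power, from 80% |
|---|---|---|---|---|
| 0 | 1.00 | 1.000 | 160 | 80.0% |
| 0.1 | 0.99 | 0.995 | 162 | 80.4% |
| 0.2 | 0.96 | 0.980 | 167 | 81.6% |
| 0.3 | 0.91 | 0.954 | 176 | 83.6% |
| 0.4 | 0.84 | 0.917 | 190 | 86.4% |
| 0.5 | 0.75 | 0.866 | 213 | 89.9% |

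**3. How much total volume already captures.** With hematoma H, edema E and total T = H + E, the variance of H left after adjusting for T is Var(H) − Cov(H,T)²/Var(T). Assume both SDs are 10 mL with correlation 0.6: Var(T) = 100 + 100 + 120 = 320, Cov(H,T) = 160, and 100 − 160²/320 = 20, so 20% is left. Over SD ratios of 2:1, 1:1 and 1:2 and correlations of 0 to 0.9, the share left runs from about 2% to 80%.

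**4. What that does to the estimate.** Continue the example with an assumed slope of 0.5 on own baseline and residual SD 10 mL. The leftover baseline has SD √20 = 4.47 mL. Its chance difference between arms has SD 4.47 × √(2/80) = 0.71 mL, which moves the treatment estimate by 0.5 × 0.71 = 0.35 mL (one SD). The residual standard error is 10 × √(2/80) = 1.58 mL. The variance ratio is 1.58² / (1.58² + 0.35²) = 0.95, a gain of about 5%. Over slopes of −0.3, 0.3 and 0.5, residual SDs of 5 to 15 mL and the ranges in step 3, the gain runs from about 0% to 33%. It stays below about 12% once residual SD is 10 mL or more.

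**5. Adding against replacing.** Simulated trials with n = 150, log-normal components (medians 10 mL hematoma and 6 mL edema, log-SD 0.8, correlation 0.6), all assumed. Entries are variance of the treatment estimate relative to adjusting for total alone.

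| Change driven by | Residual SD / explained SD | Total plus own: hematoma, edema | Own only: hematoma, edema |
|---|---|---|---|
| Own baseline | 1.5 | 0.96, 0.88 | 0.95, 0.88 |
| Own baseline | 3 | 1.00, 0.98 | 0.99, 0.97 |
| Total volume | 1.5 | 1.00, 1.01 | 1.06, 1.14 |

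Repeat runs with similar inputs moved the edema figures by one to two points. The slope cancels here, because residual SD is set as a multiple of explained SD, so a constant ratio across slopes would not show robustness. Adding the own baseline costs at most about 1%. Replacing the total loses about 6% (hematoma) and 14 to 16% (edema) if change follows the total.

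**The case against.** The strongest defence is that the covariate was chosen with reason. Protocol 4.1 describes progression as mainly dependent on the initial contusion volume, and nothing in the documents shows that a component predicts its own change better than the total does. Total volume already removes part of the component variation. This stands against replacing the total, and it limits the likely gain; it does not argue against adding a covariate that costs at most about 1% if it proves uninformative.

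A chance imbalance would also be visible: baseline hematoma and edema volumes are summarized by randomized arm (SAP 5.3), and both endpoints have subgroup analyses by those volumes. True, but a visible imbalance is not an adjusted one, and choosing covariates after seeing it is weaker than specifying them beforehand.

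Two stronger readings are tempting. A reader might infer that the planned estimates are biased; randomization rules that out on average. A reader might also infer that an imbalance would push the two estimates in opposite directions and imitate a differential mechanism. Given the total, the leftover hematoma and edema are mirror images, so this follows if both changes depend on their own baseline with the same sign. The documents give no slopes, and the endpoints are read at different times (24 and 96 hours), so it remains conjecture.

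Finally, one item in the ANCOVA sentence of SAP 5.6.1 is blacked out and material after the edema text is not shown. A supplementary analysis there cannot be excluded. The readable covariate list is nevertheless complete as a sentence.

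**Conclusion.** The point holds as an efficiency refinement to two secondary endpoints. The SAP adjusts hematoma change and edema change for baseline total volume and not for their own centrally read baselines, while the total-volume endpoints are adjusted for theirs. The consequence is possible loss of precision and weaker protection against chance imbalance in the hematoma/edema split.

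The size cannot be fixed from the documents. It is r², or 0 to 25% of residual variance for an assumed r of 0 to 0.5. In the simulated case with residual SD 1.5 times the explained SD it is about 5% for hematoma and 12 to 14% for edema, and about 3% or less when that ratio is 3. The primary analysis and its stated power are unaffected, and the protocol is not contradicted, since it names no covariates for these two endpoints.

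**What to change.** Before unblinding, state in SAP 5.6.1 and in the two endpoint paragraphs of 5.6.3 that:

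- the hematoma-change ANCOVA adds centrally read baseline hematoma volume;
- the edema-change ANCOVA adds centrally read baseline edema volume;
- each is in addition to baseline total contusion volume, not in place of it;
- total, hematoma and edema baselines never enter one model together, because they are collinear (exactly so where total is the sum);
- the total-volume models are unchanged.

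The cost is a line or two of SAP text and one degree of freedom per model. No new data are needed, and no participant with an observed change is lost, because computing the change already requires that baseline.

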4.2. Current Therapies for Brain Contusion

Brain contusion is a devastating public health problem with no approved pharmacologic treatment to stop or slow the progression of lesions following the initial trauma. The standard of care remains primarily supportive, with the maintenance of hemostasis to limit ongoing bleeding, and with surgical evacuation or other means to reduce intracranial pressure (i.e., insertion of ventricular drains, osmotherapy, or decompressive craniectomy [DC]) [Carney 2016; Haddad and Arabi 2012]. Despite these interventions, brain contusions may continue to progress, particularly during the first 12 hours following a TBI. There is no standard of care to limit HPC, leaving an urgent unmet medical need. Studies of hemostatic agents, including recombinant factor 7 and tranexamic acid, have yielded mixed results and are not routinely used in clinical practice.

CONFIDENTIAL

The information contained herein may not be used, disclosed, or published without the written consent of Biogen MA Inc.

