8. SELECTION OF PARTICIPANTS

8.1. Inclusion Criteria

To be eligible to participate in this study, candidates must meet the following eligibility criteria at Screening, or at the timepoint specified in the individual eligibility criterion listed:

1. Ability to understand the purpose and risks of the study and provide signed and dated informed consent and authorization to use confidential health information in accordance with national and local subject privacy regulations *or* consent provided by an independent physician where local regulations allow, and/or provision of informed consent by the participant's legally authorized representative (LAR) in accordance with all local and national regulations *or* according to the local ethics committee's guidelines *or* by another process compliant with applicable national laws and regulations and ethics committee requirements.
2. Aged 18 to 85 years old, inclusive, at the time of informed consent.

Note: age 18 years at the time of informed consent or participant meets the minimum age of consent in accordance with national regulations (whichever is higher).

Note: for countries where the minimum age of consent is over 18 years, participants may be enrolled provided a LAR is available, and if capable, the participant assents to treatment. The LAR must consider the participant's involvement in the study and provide informed consent for the participant.

3. A score of 5 to 15 on the GCS. Assessment should be made prior to medical intervention, where possible.

Note: an enrollment cap on participants presenting with GCS 15 will be placed at 10% of total number of participants.

4. A clinical diagnosis of brain contusion with lesions within the supratentorial brain parenchyma totaling > 3 mL in volume on noncontrast computed tomography (NCCT) scan (allowing for multiple contusions) at Screening.

Notes:

- a. Participants with multifocal contusions totaling > 3 mL in volume will be included. The sum total of contusion volumes should be calculated based on the baseline imaging.
- b. Contusion volume for a single contusion (hyperintense hematoma and hypointense edema on NCCT) must be determined and documented by the Investigator or his/her designee using study-specific methods detailed in the Imaging Manual.
- c. If more than 1 NCCT scan is performed prior to randomization, eligibility should be based on the most recent NCCT scan.

CONFIDENTIAL

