### 2.3. Sample Size Considerations

The study is planned to randomize approximately 160 participants. The primary endpoint for the study is the change in total contusion volume (hematoma plus perihematomal edema) as measured by brain imaging from baseline to 96 hours, or prior to DC, IPH evacuation, or CMO, if these procedures occur before 96 hours. Assuming the common standard deviation of 29 mL in contusion volume change from baseline, a sample size of 160 participants (40 each in the 3 mg/day dose or matching placebo arms and 40 each in the 5 mg/day dose or matching placebo arms) will have approximately 90% power to detect assumed average difference of 15 mL between the pooled active treatment groups (n=80) and pooled placebo groups (n=80) using 2 group t-test at a 2-sided significance level of 5%.

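### The imaging ANCOVAs leave out the time from injury to the baseline scan, which the trial already records: a modest, cheaply recovered loss of precision, not a bias

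*SAP*

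**What the plan says.** **Models.** SAP 5.6.1 sets one covariate list for all endpoint models: the IRT stratification factors and "baseline contusion volume per the central review and baseline GCS". SAP 5.6.2 applies that list to the primary ANCOVA. The SAP 5.6.3 entries for 24-hour contusion, 24-hour hematoma and 96-hour edema add nothing to it. The strata (SAP 3.5.1) are investigator-assessed volume class, GCS class, age class and region. No time-from-injury variable appears there, in the subgroups (3.5.2), in the primary endpoint's sensitivity analyses (5.6.2) or in the primary ANCOVA of Protocol 16.2.2.2.

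**The variable.** SAP 5.3.2 lists "Time (hours) to NCCT for eligibility post injury or LKN" among the baseline characteristics, separately from time to infusion and from the scan-to-infusion interval. It is only summarized.

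**Timing.** Protocol 4.2 says that "brain contusions may continue to progress, particularly during the first 12 hours following a TBI". Dosing may start up to 10 hours after trauma or LKN (Protocol 4.5.1), so baseline scans fall inside that period. On repeat scans, Protocol 8.1 says: "If more than 1 NCCT scan is performed prior to randomization, eligibility should be based on the most recent NCCT scan".

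**Power.** SAP 2.3 is worded "Assuming the common standard deviation of 29 mL in contusion volume change from baseline", with "approximately 90% power to detect assumed average difference of 15 mL", 80 against 80, two-sided 5%.

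**The concern.** Each imaging endpoint is a change from the pre-dose scan. If part of the growth happens in the hours when these scans are taken, an early scan leaves more of it to be counted than a late one. Baseline volume cannot separate a small lesion seen early, with growth to come, from an equally small lesion seen later in its course. Scan time supplies that information. It is fixed before treatment, so adjusting for it raises no post-randomization problem.

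Without the adjustment, variation in scan time stays in the residual and widens the intervals, and a chance difference in mean scan time between arms moves the estimate uncorrected. This is separate from whether dosing time modifies the treatment effect, which the Version 3 amendment rationale says will be explored. Two participants dosed at the same hour can have baseline scans hours apart.

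**Working it through.** **1. The plan's own figure.** Inputs from SAP 2.3: n = 80 per pooled group, difference 15 mL, SD 29 mL, two-sided 5% t-test.

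- SE = 29 × √(2/80) = 4.585 mL
- Noncentrality = 15 / 4.585 = 3.271
- Power from the noncentral t with 158 df = 90.2% (normal approximation 90.5%)

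The stated 90% is reproduced.

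**2. Effect of adding scan time.** Let R² be the share of residual variance that scan time explains, given the covariates already in the model. The documents give no value, so each R² below is an assumption. Residual SD = 29 × √(1 − R²). Equivalent extra participants = 160 × (1/(1 − R²) − 1).

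| Assumed R² | SD (mL) | SE (mL) | Power | Extra participants |
|---|---|---|---|---|
| 0% | 29.00 | 4.585 | 90.2% | 0 |
| 2% | 28.71 | 4.539 | 90.7% | 3.3 |
| 5% | 28.27 | 4.469 | 91.6% | 8.4 |
| 10% | 27.51 | 4.350 | 92.9% | 17.8 |

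The SE falls by 1.0% at R² = 2% and by 2.5% at 5%.

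**3. Break-even.** Two group means and about six covariate parameters leave 160 − 2 − 6 = 152 residual df. One more covariate repays its df once R² exceeds about 1/152 = 0.7%.

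**4. Is 2-5% plausible?** Assume that the growth remaining after a scan at t hours is proportional to 2^(−t/h), with half-life h. The share remaining at 2 h and 8 h is then 0.71 and 0.25 for h = 4, 0.79 and 0.40 for h = 6, and 0.89 and 0.63 for h = 12.

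Worked case: h = 6, scans uniform over 1-8 h, mean observed change 20 mL.

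- Mean share remaining 0.611, SD of the share 0.142
- SD of change due to scan time = 20 × 0.142 / 0.611 = 4.64 mL
- R² = 4.64² / 29² = 2.6%

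| Scan times | Mean change | h = 4 | h = 6 | h = 12 |
|---|---|---|---|---|
| 1-8 h | 20 mL | 5.7% | 2.6% | 0.65% |
| 1-8 h | 30 mL | 12.8% | 5.8% | 1.5% |
| 2-6 h | 20 mL | 1.9% | 0.8% | 0.2% |

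The half-lives, scan-time ranges and mean changes are all assumptions. The 2-5% range corresponds to wide scan times with a half-life near 6 h. Tightly grouped scans with slow decay fall below break-even. A straight line in time captures nearly all of the curve (2.54% against 2.56% in the worked case).

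**5. Chance imbalance.** In the worked case, the random difference in mean scan time between arms shifts the estimate with SD 4.64 × √(2/80) = 0.73 mL, against a target difference of 15 mL.

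**The case against.** The strongest reply is that nothing here is an error. Randomization balances scan time in expectation, and some prognostic variable is missing from every ANCOVA. The gain at 2-5% is 0.5 to 1.4 power points, the R² is assumed, and under narrow scan times it could be nil. All of this stands, and it limits the point to an inexpensive improvement.

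Other parts also stand:

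- Protocol 4.1 calls progression largely a function of initial volume, which is already in the model as a class and as a continuous central read. Volume may carry some of the information in scan time.
- Using the most recent scan, with dosing due within an hour of randomization, pulls baseline scans toward dosing. That may narrow their spread.
- The 29 mL is the SD of change. If the existing covariates lower the residual SD, baseline power is higher and a given R² adds fewer power points.
- Equal volumes meaning different things at different times suggests a volume-by-time interaction. A linear main effect is only an approximation to that.

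A reader might infer that growth is fastest in the first hours and that a late scan leaves little to measure. The documents do not support that. Protocol 4.2 says only that progression may continue, particularly in the first 12 hours. Protocol 4.5.1.3 says hemorrhagic progression and edema can occur as late as 3 to 4 days, and that hematoma and edema evolve later in contusion than in malignant infarction. Even in the assumed decay above, 25-63% of growth remains at 8 h. This weakens the case for the 96-hour endpoints.

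No visible passage makes the adjustment. Redacted exploratory text might use time, but the main-model covariate list is visible.

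**Conclusion.** The point holds as a modest loss of precision. The imaging models omit a pre-treatment variable that the trial already collects and that the protocol's own account of early progression makes plausibly prognostic. Under an assumed R² of 2-5%, power at the planned 80 per arm rises from 90.2% to about 90.7-91.6%, worth about 3-8 of 160 participants. Below about 0.7% there is no net gain.

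The case is strongest for 24-hour total contusion and 24-hour hematoma change, where early growth is a larger part of what is measured. It is weaker for the 96-hour contusion and edema endpoints. A reader might take the omission as a bias in the treatment effect or as leaving the trial underpowered. Neither follows: scan time is balanced by randomization on average, and the planned calculation meets 90% without the covariate.

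**What to change.** Before any unblinded look, including the interim analysis if it is done, add to SAP 5.6.1 the time in hours (continuous) from injury, or LKN if the injury time is unknown, to the NCCT used as the analysis baseline. Include it as a prespecified covariate in the ANCOVAs for 24-hour total contusion and 24-hour hematoma change, and in the 96-hour contusion and edema models for consistency.

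State which scan the time refers to. SAP 5.3.2 times the eligibility scan, while SAP 3.1 (Table 1) and 3.3 take the last pre-dose value as baseline. The two differ if another scan is done after eligibility and before dosing.

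The cost is one degree of freedom and a few lines of SAP text, with no new data and no site work. Measurement error when only LKN is known will reduce the gain. Missing values should be few, because the 10-hour dosing limit already requires an injury or LKN time, and SAP 5.1 drops any covariate with more than 10% missing.
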